All patients will be followed for overall survival assessment by telephone contact every 3 months from the last follow-up office visit for the remainder of time left to complete 2 years from the first dose of therapy. Patients that enter the Extension Period will be followed for overall survival assessments up to a maximum of 100 days after the last treatment dose.

Figure 3.1: Study schema

* At the completion of two years of therapy, those subjects who are benefiting and meet criteria may continue after discussion and agreement between the Investigator and Medical Monitor and will enter the Extension Period (See Section 4.3.7).

Subjects may be treated beyond PD, refer to Section 4.3.8*In Parts 3 and 4:

- nivolumab (3 mg/kg) as monotherapy will be infused over 30 minutes
- for the combination, nivolumab (1 mg/kg) will be infused over 30 minutes and after a 30-minute break, ipilimumab (3 mg/kg) will be infused over 30 minutes, then nivolumab (3mg/kg) will be infused over 30 minutes

Number of Subjects: approximately 150 subjects treated

Duration of Study: The study is expected to accrue over a period of approximately 2 years.

- maximum 28 days of screening
- At the completion of 2 years of therapy, those subjects who are benefiting and still meet study criteria may continue after discussion and agreement between the investigator and Medical Monitor and will enter the Extension Period (See Section 4.3.7)
- approximately 3 months follow-up office visits (including tumor assessments)

- 2 year overall survival assessment (by telephone contact) from first therapy dose for time remaining from last follow up office visit or for those patients that enter the Extension Period, overall survival assessments will be continued for 100 days following the last treatment dose.

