[Procedure Window ± 2 days]								
Procedure	Wk1 Day 1	Wk4 Day 1	Wk7 Day 1	Wk10 Day 1	Wk 13 Day 1 and every 2 weeks thereafter	End of Therapy	Follow- Up Visits 1 and 2^a	Notes
Pharmacokinetic Samples								
PK samples								See Table 5.5C or Table 5.5E for schedule of samples
Other Samples								
Immunogenicity blood sample (ADA)								See Table 5.5C or Table 5.5E for schedule of samples
Biomarker Samples								See Table 5.5B for schedule of samples
Efficacy Assessment								
Tumor Assessment			X		X			Subsequent assessments at week 23, then every 8 weeks thereafter. May be obtained up to 7 days prior to the required visit. CT Chest and CT or MRI abdomen, pelvis and all known sites of disease. Use same imaging method used at screening. Arm D only, MRI brain also (subjects in other arms who have stable brain metastases should have surveillance brain MRI approximately every 16 weeks and as clinically indicated).

Table 5.1D: On Treatment Procedural Outline (CA209038) - Part 2, Part 3 and Part 4: Arms A and D								
[Procedure Window ± 2 days]								
Procedure	Wk1 Day 1	Wk4 Day 1	Wk7 Day 1	Wk10 Day 1	Wk 13 Day 1 and every 2 weeks thereafter	End of Therapy	Follow- Up Visits 1 and 2^a	Notes
Survival Data Collection							X	Survival status should be continued every 3 months for the time remaining after the last office follow-up visit until 2 years from the first dose of study drug or until subject death, subject withdraws consent, subject is lost-to follow-up or the study is completed. This may be accomplished by visit or phone contact.
Clinical Drug Supplies								
IVRS drug vial assignment	X	X	X	X	X			
Nivolumab Infusion treatment	X	X	X	X	X			
Ipilimumab Infusion treatment	X	X	X	X				

^a Follow up Visit 1 and 2 will occur at 40-60 days and 101-120 days after the stop of study therapy, respectively. Efficacy is required at Follow up visit 2 only.

Table 5.1E: On Treatment Procedural Outline (CA209038) - Part 3 and Part 4: Arms B and E^a				
[Procedure Window ± 2 days]				
Procedure	Wk1 Day 1 and every 2 weeks thereafter	End of Therapy	Follow- Up Visits 1 and 2^b	Notes
Safety Assessments				
Targeted Physical Examination	X	X	X	To be performed only as clinically indicated
Vital Signs and Oxygen Saturation	X	X	X	Including BP, HR, temperature and oxygen saturation by pulse oximetry. Pulse oximetry at rest and after exertion within 72 hours prior to dosing
Physical Measurements (including performance status)	X	X	X	Weight and ECOG performance status

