7.6.8.2	Abnormal Thyroid Test	35
7.6.9	Electrocardiograms	35

7.6.10	Vital Sign and Physical Findings	35
7.6.11	Other Observations Related to Safety	36
	[REDACTED]	
7.9.1.1	Clinical Implications	42
7.9.2	Pharmacogenomics Analyses	42
8	CONVENTIONS	42
8.1	General Conventions	42
8.2	Multiple Measurements	43
8.3	Partial Dates.....	43
9	CONTENT OF REPORTS	44
	[REDACTED]	

LIST OF TABLES

Table 2.4-1:	List of Protocol Amendment.....	10
	[REDACTED]	
	[REDACTED]	
Table 5-1:	Probability that estimated ratio of on-treatment to baseline value is within 20% of true value	17
Table 5-2:	95% Exact CI for Proportion of Subjects with Increased Activated T cell On-treatment	18
Table 5-3:	95% Exact CI for Proportion of Subjects with Increased Activated T cell On-treatment	18
Table 6.2-1:	Treatment Administration.....	21

LIST OF FIGURES

Figure 6.1-1:	Study Schematic.....	19
---------------	----------------------	----

The image consists of several horizontal bands of different colors. At the top is a thick black band. Below it is a thinner white band. The main body of the image is a large black rectangular area. A small, thin white vertical line is positioned in the center of this black area. At the bottom is another thick black band. The entire image is set against a white background.

Research Hypothesis:

It is hypothesized that nivolumab (an anti-Programmed Cell Death-1 (PD-1) monoclonal antibody) and nivolumab in combination with ipilimumab will produce pharmacodynamic changes in the peripheral blood and tumor tissue of subjects with advanced melanoma (unresectable or metastatic).

Schedule of Analyses:

Final Analysis will be performed after all subjects have completed the study (after the follow-up periods) or discontinued prematurely.

Administrative interim analyses on safety, efficacy, pharmacokinetics (PK), immunogenicity, and selected biomarkers may be performed at various times prior to study completion in order to inform subsequent parts of the study, facilitate program decisions, and to support scientific

publications or presentations. Therefore, data may be reviewed prior to the final lock of the study database. No formal inferences requiring any adjustment to statistical significance level will be performed. Additional survival analysis may be performed beyond analysis for the final Clinical Study Report (CSR).

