 - ◆ Subjects whose death occurred more than 100 days after last dose of study medication without prior progression will be censored at the last tumor assessment date (prior to subsequent therapy).
 - ◆ Subjects who remain alive and have not progressed will be censored on the last tumor assessment date (prior to subsequent cancer therapy).
 - ◆ Subjects who did not have any on study tumor assessment and did not die within 100 days after last dose of study medication will be censored on the date of first dose of study medication.
 - ◆ Clinical deterioration in the absence of radiographic evidence is not considered progression for the purpose of determining PFS when using objectively documented progression.
- **Overall Survival Rate (OSR) at Month t:** The proportion of subjects surviving to time t, where t is a specific length of time, eg, 12 months, which will be determined by the available data for each interim or final analysis and will be documented in the DPP. The proportion will be calculated by the product-limit method (Kaplan-Meier estimate) which takes into account censored data.
 - Overall Survival (OS): The OS for a subject is defined as the time from the date of first dose of study medication to the date of death for any cause.
 - ◆ A subject who has not died will be censored at last known date alive.

Note: For the final CSR, investigator assessed BOR, response date and progression date (as recorded on corresponding case report form [CRF]) will be used to derive efficacy endpoints.

For administrative interim analysis (or analyses), BMS internal derived BOR, response date and progression date will be used to derive efficacy endpoints (investigator assessed BOR, response date and progression date are usually missing at the time of interim analyses).

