6.1.4 Survival Follow-up Period

All patients who do not enter the Extension Period will be followed for overall survival assessment every 3 months up to 2 years from the first dose of study therapy.

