6.1.5 Extension Period

At the completion of 2 years of therapy, those subjects who are benefiting and still meet study criteria may continue after discussion and agreement between the investigator and Medical Monitor and will enter the Extension Period. Patients that enter the Extension Period will be followed for overall survival assessments up to a maximum of 100 days after the last treatment dose.

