7.5 Efficacy

Efficacy analyses will be based on the endpoints defined in [Section 4.2.2](#) and performed on All Treated Subjects for the final analysis. Efficacy analyses based on Response Evaluable Subjects may be performed as supportive analyses. If the majority of All Treated Subjects is included in Response Evaluable Subjects, limited efficacy analyses will be performed on the Response Evaluable Subjects (eg, ORR). For interim analyses when the minimum follow-up period is less than sufficient to warrant adequate interpretation of the result, efficacy analyses may be performed on Response Evaluable Subjects.

Time to event distribution (eg, PFS, OS, and DOR) will be estimated using Kaplan-Meier (K-M) method. When appropriate, the median along with 95% CI will be provided using Brookmeyer and Crowley methodology⁷ (using log-log transformation for constructing the confidence intervals). Rates at fixed timepoints (eg, PFSR at 6 months or OS at 12 months) will be derived from the K-M estimate and the corresponding CI will be derived based from Greenwood's formula⁸. Confidence intervals for binomial proportions will be derived using the Clopper-Pearson method⁹.

Summary:

The following will be summarized by part, cohort/arm, and overall.

- The ORR with corresponding 2-sided 95% CI based on the Clopper-Pearson method, along with each category of BOR.
- The DOR with median (95% CI) and range (min, max) by K-M method. The number of subjects still in response at the time of database lock will be indicated. This summary includes responders (BOR of CR or PR) only.
- The TTR with median (95% CI) and range (min, max) by summary statistics. This summary includes responders (BOR of CR or PR) only
- The PFS and OS with median (95% CI) and range (min, max) by K-M method.
- The PFSR at specified timepoints (eg, Week 24) by K-M method.
- The OSR (eg, Month 12) by K-M method. If the number of subjects at risk is too small (eg, <5 due to high censoring), OSR will not be presented.

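### OS follow-up ends at different points inside and outside the Extension, so the late Kaplan-Meier OS curve, and any median beyond 24 months, describe a selected group and can be biased

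*SAP*

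**What the plan says.** SAP 6.1.4 sets the end of survival follow-up for one group: "All patients who do not enter the Extension Period will be followed for overall survival assessment every 3 months up to 2 years" from first dose. SAP 6.1.5 sets a different end for the other: "Patients that enter the Extension Period will be followed for overall survival assessments up to a maximum of 100 days" after the last dose. Protocol 3.1 and the synopsis give the same two limits.

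Protocol 4.3.7 admits to the Extension subjects with stable disease or a response at 2 years who tolerate nivolumab. SAP 2.1 has Extension treatment run to progression or unacceptable toxicity.

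On analysis, SAP 4.2.2 states: "A subject who has not died will be censored at last known date alive". SAP 7.5 lists "The PFS and OS with median (95% CI) and range (min, max) by K-M method" together with a KM plot of OS, by part, cohort/arm and overall, for all treated subjects. No time limit is given for either. The rule that withholds a result when about five or fewer are at risk is written for OS rates only. The rate itself is defined at a time t, "where t is a specific length of time, eg, 12 months, which will be determined by the available data".

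Other contacts exist. Follow-up office visits fall at 40-60 and 101-120 days after stopping therapy (SAP 6.1.3), and Table 5.1C provides for 12-weekly scans in Part 1. Telephone contacts are 3-monthly until 2 years: "Survival status should be continued every 3 months for the time remaining after the last office follow-up visit" (Protocol, survival rows of the Section 5.1 tables).

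**The concern.** KM assumes that subjects censored at a given time have the same outlook as those still followed. After month 24 the follow-up rules work against this twice. Those who stay under observation were chosen for doing well at 2 years. They then leave observation 100 days after stopping treatment, and stopping is triggered by progression or toxicity, so later deaths in subjects who have just done badly are mostly not counted.

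A late curve or late median would carry the label of all treated subjects in a cohort or arm while describing a progressively selected subset. The confidence interval would not reveal this, since it reflects sampling error only. OS is descriptive here, so what is at stake is the interpretation of late OS, not a test or a decision rule.

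**Working it through.** The documents give no OS assumption, event count or OS sample size, so there is no plan figure to reproduce. The check applies the written follow-up rules to assumed hazards.

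**Inputs from the documents.** 100 days = 100/30.4375 = 3.29 months (SAP 8.1 conversion). Office visit 2 at 101-120 days = 3.32 to 3.94 months after stopping, so a subject who stops at month 24 is seen to about month 28 (24 + 3.94 = 27.9).

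**Assumed inputs.** 24-month OS 55%. Of those alive, 30% or 50% extend. Death hazard per month: 0.015 to 0.04 outside the Extension; 0.005 to 0.02 on Extension treatment; 0.06 after stopping it. Stopping hazard in the Extension 0.02 per month.

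**Worked case: half extend, outside hazard 0.03, on-Extension hazard 0.005; other subjects observed to exactly month 24.**

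1. Among Extension subjects still under OS follow-up, the ratio of those stopped within 100 days to those on treatment settles at 0.02 x (1 - exp(-0.035 x 3.29))/0.035 = 0.062, where 0.035 = 0.06 - 0.005 - 0.02.
2. The hazard that KM sees is then (0.005 + 0.06 x 0.062)/1.062 = 0.0082 per month.
3. KM median = 24 + ln(0.55/0.50)/0.0082 = 24 + 0.0953/0.0082 = 35.6 months. Allowing for the first 3.3 months, when fewer have stopped, gives about 36.
4. True OS at u months after month 24 is 0.55 x [0.5 S_E(u) + 0.5 exp(-0.03u)], with S_E(u) = exp(-0.025u) + (0.02/0.035)(exp(-0.025u) - exp(-0.06u)). At u = 5.17, S_E = 0.962 and exp(-0.03u) = 0.856, so OS = 0.55 x 0.909 = 0.500. The true median is about 29 months.
5. The gap is about +7 months.

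**Range, same model.**

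| Half extend; on-Extension hazard | 0.005 | 0.01 | 0.02 |
|---|---|---|---|
| KM vs true median, outside hazard 0.03 | 36 vs 29 | 32 vs 28.5 | 28 vs 28 |
| KM vs true median, outside hazard 0.015 | 36 vs 32 | 32 vs 31 | 28 vs 29 |

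Over the full grid the median gap runs from about -1 to +9 months, and 36-month OS differs by -0.02 to +0.12.

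**Allowing for office visits.** Suppose half of the non-Extension survivors (assumed) are seen to 110 days, or 3.61 months, past month 24. In the worked case Extension subjects are then 0.5/(0.5 + 0.25) = 67% of the risk set just after month 24; with 30% extending, 0.30/(0.30 + 0.35) = 46%. The KM hazard to month 27.6 becomes about 0.68 x 0.0068 + 0.32 x 0.03 = 0.0142, using up 0.0142 x 3.61 = 0.051 of the 0.0953. The remaining 0.044 at 0.0082 takes 5.4 months. The KM median is about 33 and the gap falls from about 7 to just under 4 months. With 30% extending it falls from about 8 to just under 3. At outside hazard 0.015 the reduction is smaller (about 4 to about 3, half extending).

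**Not bounds.** Changing the stop and post-stop hazards to 0.05 and 0.10 cuts the +7 to about +2, or about +1 with office visits. A second model that follows subjects through stopping treatment, includes the late office visits and has a contact at month 24 gave KM vs true medians of 30.2 vs 26.4 and 33.5 vs 26.9 at 24-month OS of 0.544 and 0.563. At higher 24-month OS the gap was much larger (41.1 vs 28.9 at 0.588). In that model all subjects at risk at month 28.5 were Extension subjects, about 2 to 7 per 40 treated.

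**Where there is no effect.** With 24-month OS of 45% the median is about 21 months and is unaffected. KM at 12, 18 and 21 months equalled the truth in every scenario.

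**The case against.** The strongest reply has four parts.

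- **The risk set does not become an Extension-only group at month 24.** Everyone has office visits to 101-120 days after stopping, and Part 1 scans may continue. This stands: a reader might infer that everything past month 24 rests on Extension subjects, but that is safe only after about month 28.
- **The direction is not assured.** Complete responders leave treatment under Protocol 4.3.7 and 4.3.10, which removes some of the best-prognosis subjects from late follow-up. The illustrated range crosses zero, and no document figure anchors any hazard. This also stands, and is why the bias is called probable rather than shown.
- **The SAP has partial safeguards.** It gives medians only when appropriate, names no OS rate beyond 24 months, and reports extent and currentness of follow-up. These may reveal the problem. They do not correct the curve or the median, and no criterion for appropriateness is given.
- **Sampling error is larger.** At 50%, exact 95% limits are 33.8% to 66.2% for 20/40 and 18.7% to 81.3% for 5/10, wider than the illustrated difference in 36-month OS. True, but the interval shows sampling error and does not show this bias.

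A reader might also infer that estimates between months 21 and 24 are biased, because contacts are 3-monthly and no closing call is listed. The documents do not establish that. Protocol 3.1 plans a 2-year survival assessment, contacts run until 2 years, and the last known alive date draws on all appropriate CRF dates (SAP 8.1). If a gap did exist its sign would depend on reporting: with half of the non-Extension subjects observed to month 24, the 24-month estimate was 0.556 vs 0.550 if later deaths were missed and 0.544 vs 0.550 if only deaths were reported late. This is a matter for clarification.

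**Conclusion.** The concern holds for the late OS curve and for a median beyond 24 months. The written rules make the post-24-month risk set increasingly selected and its censoring informative, and the SAP places no limit on reporting there. The bias is probably upward. At an assumed 24-month OS of 55% the median gap was about -1 to +9 months, less with late office visits; this is an illustration under the stated hazards and uptake, not an estimate for this trial. The median is affected only if 24-month OS exceeds 50%. Estimates to month 21, including the SAP's example 12-month rate, are unaffected. Because OS is descriptive, the consequence is confined to how late OS is read. It is worth correcting because the correction is cheap.

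**What to change.** In SAP 4.2.2 and 7.5, report the OS curve, median and rates by cohort/arm to a common 24-month horizon. Censor subjects alive then at 24 months, and give the median as *not reached* if the curve stays above 50%. Keep the untruncated curve as a supplementary figure, with numbers at risk and a note that the part after 24 months reflects a selected, mainly Extension, group.

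Separately, clarify in Protocol 3.1 and Tables 5.1C-E that the last survival contact falls at or just after month 24, so that vital status is known at the horizon.

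Cost: SAP wording and one clarifying line in the protocol. If the contact is not already made, it is at most one extra or re-timed call per surviving non-Extension subject: 150 x 0.45 x 0.5 = 34 to 150 x 0.55 x 0.7 = 58 calls, taking 45-55% alive at month 24 and 30-50% of them extending (assumed). The downside is that there is no main OS estimate beyond 24 months; later Extension deaths stay visible in the supplementary curve.

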6.2 Treatment Regimens

Treatment administration for nivolumab and ipilimumab (a \pm 2-day window will be allowed) is provided in Table 6.2-1.

The treatment group “as assigned” will be retrieved from the IVRS system for subjects who were assigned (Parts 1 and 2) or randomized (Parts 3 and 4) to a group. The treatment group “as treated” is expected to be the same as the arm as randomized by IVRS. However, if a subject received the incorrect drug for the entire period of treatment, this will be documented as a relevant protocol deviation (see [Section 7.2.3](#)) and the subject’s treatment group will be defined as the incorrect drug the subject actually received. For example, if a subject was randomized to the combination therapy, but only received nivolumab monotherapy for the entire treatment duration, they will be put into the nivolumab monotherapy treatment group.

6.3 Populations for Analyses

- All Enrolled Subjects: All subjects who signed an informed consent form and were registered into the IVRS.
- All Treated Subjects: All subjects who received at least one dose of study medication
- Pharmacokinetic Subjects: All subjects who received at least one dose of study medication and have available serum concentration data
- Response Evaluable Subjects: All treated subjects with measurable disease at baseline and one of the following: 1) at least one post-baseline tumor assessment, 2) clinical progression, or 3) death (if death occurred within 100 days after last dose of study medication)
- Immunogenicity Subjects:
 - Nivolumab ADA Evaluable Subjects: All treated subjects with baseline and at least 1 post-baseline nivolumab immunogenicity assessment.
 - Ipilimumab ADA Evaluable Subjects: All treated subjects with baseline and at least 1 post-baseline ipilimumab immunogenicity assessment.
- Biomarker Evaluable Subjects: All Treated Subjects with at least one evaluable measurement for a specific marker will be included in the dataset for that marker. Evaluable may differ depending on the analysis.

Table 6.2-1: Treatment Administration

Cohort/ Arm	Dose	Infusion Time	Population
1 and 2	3 mg/kg nivolumab every 2 weeks	60 minutes	Cohort 1: ~40 anti-CTLA4 naive subjects Cohort 2: ~40 anti-CTLA4 progressed subjects
A	1 mg/kg nivolumab + 3 mg/kg ipilimumab every 3 weeks x 4 doses And then 3 mg/kg nivolumab	Part 2: nivolumab 60 minutes + 30 minutes break + ipilimumab 90 minutes And then nivolumab 60	Anti-CTLA4 naive only ~10 subjects with biopsy window between Days 8 and 15 ~10 subjects with biopsy

Table 6.2-1: Treatment Administration

Cohort/ Arm	Dose	Infusion Time	Population
	every 2 weeks	minutes Part 3: nivolumab 30 minutes + 30 minutes break + ipilimumab 30 minutes And then nivolumab 30 minutes	window between Days 22 and 29 Anti-CTLA4 naive only ~20 reduced infusion subjects
B	3 mg/kg nivolumab every 2 weeks	30 minutes	Anti-CTLA4 naive only ~10 reduced infusion subjects
D	1 mg/kg nivolumab + 3 mg/kg ipilimumab every 3 weeks x 4 doses And then 3 mg/kg nivolumab every 2 weeks	Nivolumab 30 minutes + 30 minutes break + ipilimumab 30 minutes And then nivolumab 30 minutes	Anti-CTLA4 naive only ~10 reduced infusion subjects with brain metastases
E	3 mg/kg nivolumab every 2 weeks	30 minutes	Anti-CTLA4 naive only ~10 reduced infusion subjects with brain metastases

